2.4 Secondary endpoints

2.4.1 Supportive secondary endpoints

For all supportive secondary endpoints, meal-time fast-acting insulin aspart will be compared to meal-time NovoRapid®, and post-meal fast-acting insulin aspart will be compared to meal-time NovoRapid®. Change from baseline refers to the change from randomisation to 26 weeks after randomisation.

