2.4.1.2 Safety endpoints

All safety endpoints will be compared using the on treatment observation period. In terms of adverse events, as a minimum, serious adverse events will be tabulated separately also using the in trial observation period.

All events in the in trial observation period will be listed with information about whether it appeared in the on treatment observation period or not.

Classification of Hypoglycaemia:

Treatment emergent: hypoglycaemic episodes will be defined as treatment emergent if the onset of the episode occurs on or after the first day of treatment with investigational medicinal product (IMP) after randomisation, and no later than 1 day after the last day on IMP.

Nocturnal hypoglycaemic episodes: are episodes occurring between 23:00 and 07.00 both inclusive.

[figure not shown]
Hypoglycaemic episodes are classified according to ISPAD's definition of severe hypoglycaemia⁴, as well as Novo Nordisk classification of hypoglycaemia (see [Figure 2-1](#)) and the ADA classification of hypoglycaemia⁵ (see [Figure 2-2](#)).

Novo Nordisk classification of hypoglycaemia in paediatrics

In normal physiology, symptoms of hypoglycaemia occur below a PG level of 3.1 mmol/L (56 mg/dL)⁶. Therefore, Novo Nordisk has included hypoglycaemia with PG levels below this cut-off point in the definition of blood glucose (BG) confirmed hypoglycaemia.

Novo Nordisk uses the following classification (see [Figure 2–1](#)) in addition to the ADA classification:

- Severe hypoglycaemia according to the ISPAD classification⁴: Was the hypoglycaemic episode associated with severe neuroglycopenia, usually resulting in coma or seizure and requiring parenteral therapy (glucagon or intravenous glucose)?
- Symptomatic BG confirmed hypoglycaemia: An episode that is BG confirmed by PG value $< 3.1 \text{ mmol/L (56 mg/dL)}$ **with** symptoms consistent with hypoglycaemia.
- Asymptomatic BG confirmed hypoglycaemia: An episode that is BG confirmed by PG value $< 3.1 \text{ mmol/L (56 mg/dL)}$ **without** symptoms consistent with hypoglycaemia.
- Severe or BG confirmed symptomatic hypoglycaemia: An episode that is severe according to the ISPAD classification⁴ or BG confirmed by a PG value $< 3.1 \text{ mmol/L (56 mg/dL)}$ **with** symptoms consistent with hypoglycaemia.
- BG confirmed hypoglycaemia: An episode that is BG confirmed by a PG value $< 3.1 \text{ mmol/L (56 mg/dL)}$ **with or without** symptoms consistent with hypoglycaemia.

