- Severe or BG confirmed hypoglycaemia: An episode that is severe according to the ISPAD classification⁴ or BG confirmed by a PG value $< 3.1 \text{ mmol/L (56 mg/dL)}$ **with or without** symptoms consistent with hypoglycaemia.

[figure not shown]

Note: Glucose measurements are performed with capillary blood calibrated to plasma equivalent glucose values

Figure 2–1 Novo Nordisk classification of hypoglycaemia in paediatrics

ADA⁵/ISPAD classification of hypoglycaemia in paediatrics

- Severe hypoglycaemia according to the ISPAD classification⁴: Was the hypoglycaemic episode associated with severe neuroglycopenia, usually resulting in coma or seizure and requiring parenteral therapy (glucagon or intravenous glucose)?
- Asymptomatic hypoglycaemia: An episode not accompanied by typical symptoms of hypoglycaemia, but with a measured PG concentration ≤ 3.9 mmol/L (70 mg/dL).
- Documented symptomatic hypoglycaemia: An episode during which typical symptoms of hypoglycaemia are accompanied by a measured PG concentration ≤ 3.9 mmol/L (70 mg/dL).
- Pseudo-hypoglycaemia: An episode during which the person with diabetes reports any of the typical symptoms of hypoglycaemia with a measured PG concentration > 3.9 mmol/L (70 mg/dL) but approaching that level.
- Probable symptomatic hypoglycaemia: An episode during which symptoms of hypoglycaemia are not accompanied by a PG determination but that was presumably caused by a PG concentration ≤ 3.9 mmol/L (70 mg/dL).

Note: Glucose measurements are performed with capillary blood calibrated to plasma equivalent glucose values

Figure 2–2 ADA/ISPAD classification of hypoglycaemia in paediatrics

The following safety endpoints will be assessed:

- Number of treatment emergent hypoglycaemic episodes
 - According to ADA/ISPAD classification
 - According to Novo Nordisk/ISPAD classification
- Number of treatment emergent hypoglycaemic episodes subdivided into daytime and nocturnal (23:00-7:00, both included)
 - According to ADA/ISPAD classification
 - According to Novo Nordisk/ISPAD classification
- Number of treatment emergent meal related (from start of meal until 1, 2, and 4 hours after start of meal and from 1 [exclusive] to 2 hours [inclusive], 2 [exclusive] to 3 hours [inclusive], 3 [exclusive] to 4 hours [inclusive], and from 2 hours [exclusive] to 4 hours [inclusive] after start of meal, respectively) hypoglycaemic episodes
 - According to ADA/ISPAD classification
 - According to Novo Nordisk/ISPAD classification

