Data on treatment emergent hypoglycaemic episodes are presented in terms of the number of Subjects with at least one event (N), the percentage of Subjects with at least one event (%), the number of events (E) and the event rate per 100 years of exposure (R). Separate summaries are made by severity (the ISPAD criterion for severe hypoglycaemia⁴) considering all episodes, nocturnal and daytime episodes using Novo Nordisk and ADA classified episodes. Episodes will also be summarised overall and by category in relation to time since start of meal, as occurring within the following time intervals:

- During first 1, 2, and 4 hours after start of meal
- Between 1 (exclusive) to 2 hours (inclusive) after start of meal
- Between 2 (exclusive) to 3 hours (inclusive) after start of meal
- Between 3 (exclusive) to 4 hours (inclusive) after start of meal
- Between 2 hours (exclusive) to 4 hours (inclusive) after start of meal

Non-treatment emergent hypoglycaemic episodes will be listed.

The number of treatment emergent severe or BG confirmed hypoglycaemic episodes (all, daytime, nocturnal) will be analysed using a negative binomial regression model with a log-link function and the logarithm of the time period for which a hypoglycaemic episode is considered treatment emergent as offset. The model will include treatment, region and strata as factors, and will be based on the FAS. To the extent where data allow, separate analyses will be performed for severe episodes (all).

- Number of treatment emergent adverse events (AEs)

AEs will be coded using the Medical Dictionary for Regulatory Activities (MedDRA). AEs will be presented based on system organ class and preferred terms.

A Treatment Emergent Adverse Event (TEAE) is defined as an event that has an onset date on or after the first day of exposure to randomised treatment, and no later than 7 days after the last day of randomised treatment.

TEAEs are summarised descriptively, whereas AE's not defined as treatment emergent are presented in listings, including AEs reported in the 30-day follow-up period. The summaries of TEAEs are made displaying the number of Subjects with at least one event, the percentage of Subjects with at least one event, the number of events and the event rate per 100 Subjects years of exposure. These summaries are done by seriousness, severity, relation to insulin treatment, relation to device, withdrawal due to AEs and outcome.

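### The first hour after a meal, where the adult type 1 trial found a hypoglycaemia excess, is tabulated but has no pre-specified adjusted rate ratio or confidence interval

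*SAP*

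**What the plan says.** **Prior evidence.** Protocol 3.4 describes the adult basal-bolus trial in type 1 diabetes. Severe or BG confirmed episodes did not differ significantly overall. In the first hour after the start of a meal, a smaller fraction of all episodes, the rate was significantly higher with meal-time faster aspart. No rate, ratio or interval is given.

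**Endpoint and table.** SAP 2.4.1.2 lists meal-related episodes, including those from 0 to 1 h, among the safety endpoints. All treatment emergent hypoglycaemia is presented as subjects affected (N), percentage, number of episodes (E) and rate per 100 years of exposure (R). For the meal windows the text is: "Episodes will also be summarised overall and by category in relation to time since start of meal". SAP section 3 adds the 1-2, 2-3 and 3-4 h windows to look further at safety, but adds no model for them.

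**Model.** "The number of treatment emergent severe or BG confirmed hypoglycaemic episodes (all, daytime, nocturnal) will be analysed using a negative binomial regression model". It has a log-exposure offset, with treatment, region and strata as factors, on the FAS. Severe episodes are analysed separately where data allow. No meal window is named.

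**General text.** SAP 2.4.1 states: "For all supportive secondary endpoints, meal-time fast-acting insulin aspart will be compared to meal-time NovoRapid", and likewise for the post-meal arm. SAP 2.4.1.2 states: "All safety endpoints will be compared using the on treatment observation period". The general considerations in SAP section 2 give differences or ratios with 95% intervals for endpoints that are analysed statistically.

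**The concern.** The plan models the category that showed no significant difference in adults and tabulates the one that did. A faster early insulin action makes the first hour the natural place to look in children too.

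At stake is whether the report will contain a comparative estimate for that hour, chosen before the data are seen and adjusted for region and age stratum as the overall rate is. Without one, any interval would have to be built after the fact, and the choice among the seven listed windows (0-1, 0-2, 0-4, 1-2, 2-3, 3-4 and 2-4 h) would be open to being driven by the data.

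**Working it through.** **The plan's own figures.** The documents contain no power, rate or precision statement for hypoglycaemia. The only design calculation is for HbA1c, with 250 per arm and SD 1.3. The standard error is 1.3 × sqrt(2/250) = 0.1163. Step 1: Phi(0.40/0.1163 − 1.96) = 93.1%. Step 2: Phi(0.35/0.1163 − 1.96) = 85.3%. With the t-distribution they are 93.0% and 85.2%, against the stated figures of more than 93% and 85%. This confirms the 250 per arm used below and says nothing about hypoglycaemia.

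**Does any text give the window an estimate?** The model sentence has a closed list: all, daytime, nocturnal, then severe. The window sentence says summarised. The two general sentences say compared but name no model, ratio or interval for the windows. The promise of intervals attaches to endpoints analysed statistically, which the windows are not. So none is pre-specified.

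**Dilution.** Let f be the share of episodes in the first hour, with a true ratio of 1.5 there and 1 elsewhere. The all-episode ratio is 1 + f × (1.5 − 1). The documents give no f.

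- f = 5%: 1.025
- f = 10%: 1.05
- f = 20%: 1.10

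If episodes only move earlier, the overall ratio can be null. For example, with 10% of episodes at 0-1 h and ratio 1.5, and 30% at 2-4 h and ratio 5/6: 1 + 0.10 × 0.5 − 0.30 × 1/6 = 1.00.

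**What the model would deliver.** Assumed inputs: 250 per arm, 0.5 years each, control first-hour rate 0.5 to 3 per subject-year, dispersion k from 1.5 to 4. With mu = rate × 0.5 and true ratio RR:

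- SE of log ratio = sqrt((1/mu + 1/(RR × mu) + 2k)/250)
- interval = estimate divided and multiplied by exp(1.96 × SE)
- power = Phi(ln RR/SE − 1.96)

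| Rate, k | Control episodes | SE at 1.5 | Interval factor | Power at 1.5 | Power at 1.25 |
|---|---|---|---|---|---|
| 0.5, 4 | 62.5 | 0.242 | 1.61 | 39% | 15% |
| 0.5, 1.5 | 62.5 | 0.197 | 1.47 | 54% | 20% |
| 1, 3 | 125 | 0.193 | 1.46 | 56% | 21% |
| 2, 2 | 250 | 0.151 | 1.34 | 77% | 31% |
| 3, 4 | 375 | 0.191 | 1.45 | 57% | 21% |
| 3, 1.5 | 375 | 0.128 | 1.29 | 89% | 41% |

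If 20% of episodes lacked a meal time, power at 1.5 would be 35% to 86%.

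**What the planned table already allows.** Under a negative binomial, the proportion with no episode is (1 + k × mu)^(−1/k). N gives that proportion and E gives mu, so k can be solved for. In simulation of the six cases (4,000 trials each, ratio 1.5), an interval built only from N and E covered the true ratio 94.7% to 95.6% of the time. It is unadjusted, assumes equal exposure and relies on the negative binomial form.

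**The case against.** The strongest reply is that little is lost. The table shows rates by arm, randomisation makes those crude rates comparable, and N with E supports an approximate interval. The added windows would show whether episodes move earlier. Describing supportive safety endpoints without a model is also consistent here: TEAEs, injection site reactions, vital signs and antibodies are all descriptive. And if the true ratio is nearer 1.25 than 1.5, the model would usually be non-significant and could be misread as reassurance.

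Most of this stands, and it limits the point. A reader might infer that the table hides a first-hour excess or cannot yield a valid interval. The documents do not support either: N and E are both printed, and the check above recovers an interval with nominal coverage. A reader might also object to a Poisson interval from E and exposure, but the SAP plans none.

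What does not fall is the asymmetry. Hypoglycaemia, unlike those other endpoints, already has a model in the SAP, and the first-hour window is the one with a documented prior signal. An interval reconstructed by a reader is neither pre-specified nor adjusted for region and strata.

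**Conclusion.** The point holds as a cheap improvement. The first-hour window has a reported adult signal and is a listed endpoint, yet it has no pre-specified, covariate-adjusted rate ratio or interval. The all-episode ratio is a poor substitute, since a first-hour ratio of 1.5 would shrink to 1.025-1.10 under the assumed shares.

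Every rate, dispersion, share and effect size above is an assumption. What rests on the documents alone is the scope of the model and the adult finding. It would be wrong to read this as a threat to the confirmatory conclusions: the HbA1c hierarchy and its error control are untouched. It would also be wrong to read the general statements that endpoints will be compared as contradicting the plan; they simply leave the method for these windows open.

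**What to change.** Add to SAP 2.4.1.2, with the qualifier already used for severe episodes (as far as data allow):

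- Apply the existing negative binomial model (treatment, region, strata, log-exposure offset, FAS) to treatment emergent severe or BG confirmed episodes 0-1 h after the start of a meal.
- Apply it alongside to the listed window "Between 2 hours (exclusive) to 4 hours (inclusive) after start of meal", so that a shift in timing is not read as a net excess.
- Report rate ratios with 95% intervals against meal-time NovoRapid, primarily for the meal-time arm. For the post-meal arm, note that it is open-label and injects 20 minutes after meal start, so 0-1 h covers only about 60 − 20 = 40 minutes after injection.
- Label the results supportive and unadjusted for multiplicity, and state that a non-significant result is not evidence of no excess.
- Report episodes with missing meal time by arm. If a window is too sparse to fit, keep the planned table and say so.

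**Cost.** Some SAP wording and four extra contrasts (two windows, two comparisons). No new data are needed, because the episode record in Protocol 8.5.1.1 includes the time of the last meal. The downsides are more unadjusted safety comparisons and precision that depends on unknown rates and dispersion. The model may also fail to fit with region and four age strata, since SAP section 3 notes few subjects under 3 years. Some late-reported non-severe episodes will lack a meal time, which Protocol 8.5.1.1 says the sponsor will not query.

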8.1.4 Randomisation

Randomisation (Visit 14) should occur after the 12-week run-in period has been completed. If the Subject meets the randomisation criteria and none of the run-in failure criteria, the Subject will be randomised into one of the three treatment arms by using IV/WRS, as described in section [10](#). The Subject will keep the same Subject number as allocated at screening. Stop date of NovoRapid® from run-in and start date of the randomised trial product will be recorded in the eCRF.

In the morning of Visit 14 the Subject should collect a capillary blood sample for FPG central laboratory analysis using the FPG home sampling kit provided at Visit 12. The Subject must be fasting for the capillary FPG blood sample, as described in section [8.6.4](#). If the Subject has performed the FPG blood sampling at home fasting is not required for Visit 14. Subjects participating in the CGM and meal test subgroup must attend Visit 14 fasting, as described in section [8.1.7](#) and in [Appendix B](#).

Subjects must attend Visit 14 without having taken any insulin for at least 8 hours prior to the visit as required for insulin antibody blood sampling.

For randomisation visit procedures (Visit 14), see flowchart, section [2](#).

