8.5.1.1 Hypoglycaemic episodes

Plasma glucose should always be measured and recorded when a hypoglycaemic episode is suspected.

All plasma glucose values:

- ≤ 3.9 mmol/L (70 mg/dL) or
- > 3.9 mmol/L (70 mg/dL) occurring in conjunction with hypoglycaemic symptoms

should be reported in the diary according to the instructions below throughout the trial from Visit 2 to Visit 41. Upon onset of a hypoglycaemic episode the Subject is recommended to measure plasma glucose every 15 minutes until the SMPG value is > 3.9 mmol/L (70 mg/dL) or symptoms have been resolved in accordance to current guidelines^{[35](#)}.

A SMPG value ≤ 3.9 mmol/L (70 mg/dL) or hypoglycaemic symptoms must trigger a hypoglycaemic episode form to be completed by the Subject. Repeated SMPG measurements and/or symptoms will per default be considered as one hypoglycaemic episode until a succeeding SMPG value is > 3.9 mmol/L (70 mg/dL) and/or symptoms have been resolved. One hypoglycaemic episode form is to cover these measurements and/or symptoms. However, each hypoglycaemic episode form will cover a period of maximum 60 minutes after onset of a hypoglycaemic episode.

In case of several low SMPG values within the 60 minutes interval, the lowest value is the one that will be reported as the SMPG value for the hypoglycaemic episode but the start time of the episode will remain as the time for the first SMPG value and/or symptom.

If a new low SMPG value is measured or the Subject still has symptoms more than 60 minutes after the first reported low SMPG value and/or symptom it is considered as a new hypoglycaemic episode and a new hypoglycaemic episode form is to be filled in.

The record should include the following information:

- Start date and time of hypoglycaemic episode
- Time and value of plasma glucose level before treating the episode (if available) and any follow up measurements.

The lowest value measured during the hypoglycaemic episode will be reported as the plasma glucose value for the episode, the remaining values will be kept as source data.

- Whether the episode was symptomatic (Yes/No)

A hypoglycaemic episode starting without symptoms should be updated to symptomatic if the Subject experience symptoms later during the episode.

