The trial includes a screening visit to assess the Subject's eligibility. At Visit 2, the eligible Subjects will be enrolled in a 12-week run-in period where all Subjects will be switched from their previous insulin treatment to insulin degludec once daily and meal-time NovoRapid®. During the 12-week run-in period the Investigator will focus on optimisation of the basal insulin on a weekly basis to individual fasting plasma glucose (FPG) targets. After the run-in period, Subjects with HbA_{1c} \leq 9.5% (80 mmol/mol) who based on the Investigator's judgement have shown ability and willingness to adhere to the trial protocol will be randomised (1:1:1) to receive meal-time fast-acting insulin aspart, post-meal fast-acting insulin aspart or meal-time NovoRapid®, all in combination with insulin degludec. Here, Meal-time dosing is defined as injecting 0 - 2 minutes before the meal, and Post-meal dosing, is defined as injecting 20 minutes after the start of the meal.

¹ In the protocol fast-acting insulin aspart was referred to as faster-acting insulin aspart.

[figure not shown]

Figure 1–1 Trial design

In order to ensure a comparable number of Subjects of similar age in each treatment group the randomisation is stratified by age at randomisation according to the following categorisation: $1 \leq \text{age} < 3$ years, $3 \leq \text{age} < 6$ years, $6 \leq \text{age} < 12$ years and $12 \leq \text{age} < 18$ years. This categorisation of age will henceforth be referred to as strata.

Subjects prematurely discontinued from trial product should continue with the per protocol planned visits after 12 weeks (Visit 26) and 26 weeks (Visit 40) from randomisation depending on when the Subject discontinues trial product.

For further details on handling of Subjects that prematurely discontinue from trial product and the trial in general, please see the trial protocol.

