1.2 Scope of the statistical analysis plan

This statistical analysis plan (SAP) is based on the protocol *Efficacy and Safety of Faster-acting insulin aspart compared to NovoRapid® both in Combination with Insulin Degludec in Children and Adolescents with Type 1 Diabetes*, version 5.0 (dated 16 January 2017). The statistical analyses and derivations of endpoints presented in this SAP are almost identical to those described in the protocol. It contains minor clarifications for derivations, calculation of endpoints and analyses as well as a few additions.

The changes to the statistical considerations proposed in this SAP and the reasons for the changes are described in section [3](#) and will be reported in the clinical trial report (CTR).

2 Statistical considerations

General considerations

In general, for endpoints evaluated as a change from baseline and/or where a baseline adjustment is made, baseline is defined as information collected at the randomisation visit (Visit 14). In case a measurement is not available at the randomisation visit, the most recent measurement prior to the randomisation visit will be used as baseline.

Two observation periods are defined, “in trial” and “on treatment”, and it will be specified which period each analysis will use.

- In trial: the observation period from date of randomisation and until last trial -related Subject-site contact. The in trial observation period includes data collected after treatment discontinuation.
- On treatment: the observation period from date of first dose of randomised NovoRapid®/fast-acting insulin aspart and no later than 7 days after the day of last dose of NovoRapid®/fast-acting insulin aspart. The on treatment observation period includes data collected up to and including 7 days after treatment discontinuation.

All primary and secondary efficacy endpoints will be summarised and analysed using the full analysis set (FAS), unless otherwise stated. Safety endpoints will be summarised using the safety analysis set (SAS) and analysed using the FAS, unless otherwise stated.

Presentation of results from a statistical analysis will include the estimated mean treatment effects (LSMeans) for change from baseline, if applicable. Estimated mean treatment differences (or ratios) will be presented together with two-sided 95% confidence intervals for all endpoints analysed statistically.

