For endpoints measured over time mean values will be plotted to explore the trajectory over time. For survival endpoints, e.g. drop-out pattern, Kaplan-Meier plots are presented for each treatment.

Data collected before randomisation (Visit 14) will only be summarised descriptively.

Selected tables and figures will also be presented by age group, where age group refers to the following categorisation of age: $1 \leq \text{age} < 6$ years, $6 \leq \text{age} < 12$ years and $12 \leq \text{age} < 18$ years.

Testing strategy and estimands

The primary objective, confirming the effect of treatment with meal-time fast-acting insulin aspart in children and adolescents with type 1 diabetes will be assessed using a non-inferiority approach comparing the change from baseline HbA_{1c} to meal-time NovoRapid®, where both treatments are

combined with insulin degludec. More specifically the upper limit of the 95% confidence interval should be compared to a non-inferiority margin of 0.4. If it is below or equal to 0.4 non-inferiority will be considered established and the effect demonstrated.

The trial also aims to confirm the effect of treatment with post-meal fast-acting insulin aspart and to confirm superiority of meal-time fast-acting insulin aspart both in combination with insulin degludec in children and adolescents with type 1 diabetes. In order to control the family-wise type I error rate in the strong sense, a hierarchical (fixed sequence) testing procedure will be deployed. This is based on a priority ordering of the null-hypotheses, and testing them in this order using the two-sided 95% confidence interval approach until an insignificant result appears. The effect is that rejection of the null hypothesis will only be confirmed for analyses where all previous null-hypotheses have been rejected in favour of fast-acting insulin aspart. This is done using a hierarchical testing procedure with three steps:

Step 1: HbA_{1c} non-inferiority of meal-time fast-acting insulin aspart versus meal-time NovoRapid® both in combination with insulin degludec

Step 2: HbA_{1c} non-inferiority of post-meal fast-acting insulin aspart versus meal-time NovoRapid® both in combination with insulin degludec

Step 3: HbA_{1c} superiority of meal-time fast-acting insulin aspart versus meal-time NovoRapid® both in combination with insulin degludec

Primary estimand

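### The hypoglycaemia rate model leaves out each subject's own run-in episode rate, which is already collected and could tighten the rate-ratio interval a little

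*SAP*

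**What the plan says.** SAP 2.4.1.2 analyses the number of treatment-emergent severe or BG confirmed episodes (all, daytime, nocturnal) by negative binomial regression with a log link and log time at risk as offset. On the terms it says: "The model will include treatment, region and strata as factors, and will be based on the FAS". Protocol 17.4.1.2, as changed by Amendment 4, has the same terms.

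Run-in episode data exist for the same subjects:

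- From Visit 2, "all Subjects will be switched from their previous insulin treatment to insulin degludec once daily and meal-time NovoRapid" (SAP 1.1).
- Low glucose values and symptomatic episodes "should be reported in the diary according to the instructions below throughout the trial from Visit 2 to Visit 41" (Protocol 8.5.1.1).
- Randomisation "should occur after the 12-week run-in period has been completed" (Protocol 8.1.4).

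Two general rules in SAP section 2 bear on their use. Baseline means Visit 14 information, or the latest earlier measurement if none is available at that visit. And: "Data collected before randomisation (Visit 14) will only be summarised descriptively".

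**The concern.** A subject's past episode rate is a natural predictor of the later rate. Here it is measured before allocation, under one regimen, so treatment cannot have affected it. Elsewhere the modelled endpoints carry a baseline covariate: the SMPG, FPG and 1,5-anhydroglucitol analyses, the HbA1c responder analyses, the modelled CGM and meal-test endpoints, body measurements and lipids. The episode count is the exception, and the SAP gives no reason.

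The stakes are limited. Hypoglycaemia has no margin, no power statement and no place in the three-step hierarchy. It is, however, the only safety event count with a formal comparison between arms: adverse events are summarised descriptively and injection site reactions have no formal analysis. A wider interval than necessary for each faster aspart arm is the whole of the possible loss.

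**Working it through.** **Stated figures.** The plan gives none for hypoglycaemia. Its only power figures, for HbA1c (more than 93% and 85%), reproduce by noncentral t with 250 per arm and SD 1.3 (93.0% and 85.2%). They are not affected by this point.

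**Inputs from the documents.** 1:1:1 allocation, 250 per arm (SAP 2.1); 12-week run-in and 26-week treatment (SAP 1.1); four age strata.

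**Inputs assumed.** 2, 5 or 20 episodes per subject-year; frailty variance 1; four regions; correlation between the latent run-in and treatment frailties of 0 to 0.7; true rate ratio 1.

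**Without the covariate.** With expected treatment-period count μ and dispersion k, approximately

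SE(log RR) = √[(2/n)(1/μ + k)].

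At 20 per year, μ = 20 × 26/52 = 10, so SE = √[(2/250)(0.1 + 1)] = 0.094. At 5 per year, μ = 2.5 and SE = √[0.008 × 1.4] = 0.106. The simulated values below agree. A covariate can reduce only the k part, not 1/μ.

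**With the covariate.** Trials were simulated and fitted by negative binomial maximum likelihood, with region and strata in both models, with and without log((run-in count + 0.5)/run-in time), 1,500 replicates per cell. Model SE under gamma frailty:

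| Episodes per year | No covariate | Corr. 0.3 | Corr. 0.5 | Corr. 0.7 |
|---|---|---|---|---|
| 2 | 0.124 | 0.124 | 0.122 | 0.120 |
| 5 | 0.105 | 0.103 | 0.101 | 0.097 |
| 20 | 0.093 | 0.091 | 0.087 | 0.079 |

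At correlation 0.5 the falls are 0.002/0.124 = 1.6%, 0.004/0.105 = 3.8% and 0.006/0.093 = 6.5%. At 0.7 they are 3.2%, 7.6% and 15.1%. At 0.3 they run from below the rounding to about 2%. At 0 there is no gain. With gamma variance 0.5 or 2 (500 replicates) the falls are 0.7-6.9% at 0.5 and 1.5-15.6% at 0.7.

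**95% intervals around a ratio of 1**, exp(±1.96 SE), at correlation 0.5:

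- 20 per year: 0.83-1.20 becomes 0.84-1.19
- 5 per year: 0.81-1.23 becomes 0.82-1.22
- 2 per year: 0.78-1.28 becomes 0.79-1.27

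The gain is small at 2 per year because the expected run-in count is only 2 × 12/52 = 0.46. With gamma frailty of variance 1, 1/(1 + 0.46) = 0.68, so about two thirds of subjects have no run-in episode.

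**Fall in actual sampling SD of the log rate ratio:**

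| Frailty | Corr. | 2/yr | 5/yr | 20/yr |
|---|---|---|---|---|
| Gamma | 0.5 | 1.0% | 3.1% | 4.5% |
| Gamma | 0.7 | 2.8% | 6.9% | 10.9% |
| Lognormal | 0.5 | 2.3% | 4.9% | 9.8% |
| Lognormal | 0.7 | 4.2% | 9.5% | 20.0% |

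A fall of 1.0-4.5% is worth 1/0.99² = 1.02 to 1/0.955² = 1.10, or 2-10% more subjects.

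**Cross-check.** A separate simulation used lognormal frailty without region or strata, dispersion 0.6 and 1.2, and 60 trials per cell. The model SE fell by 0% at correlation 0. At 2 per year it fell by 0.1-0.4%, 0.7-1.3% and 1.4-2.8% at correlations 0.3, 0.5 and 0.7. At 10 per year it fell by 1.3-1.5%, 4-5% and 8-10%. At the extreme of 40 per year and correlation 0.9 the fall was 31-34%.

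**Coverage of the model-based 95% interval.** Gamma frailty: 0.947-0.955 without the covariate and 0.936-0.955 with it. Lognormal frailty: 0.90-0.95 in both models, lowest at 20 per year.

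**The case against.** The planned model is complete and prespecified, and the endpoint is supportive. Every input that drives the gain is assumed, and at a correlation of 0.5 the intervals move only in the second decimal. All of that stands. For infrequent episodes the gain is about 0-3%.

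Run-in may also predict treatment poorly. Basal insulin is titrated in run-in and bolus insulin afterwards (Protocol 5.1, 5.3.2). Run-in also starts with a switch of both insulins, with dose reductions considered individually (Appendix A 3.1), and includes reinforced diabetes training (Protocol 8.7.2). Amendment 4 corrected the diary wording for severe episodes, so some subjects' two counts may fall under different wording. That matters only for severe episodes without a PG value below 3.1 mmol/L, since the others count as BG confirmed anyway. These limits stand. They lower a correlation whose zero case gives no gain and, in the simulations, no loss.

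The largest gains, under lognormal frailty at 20 per year, arise where coverage is about 0.90 without the covariate and 0.90-0.925 with it. The covariate does not repair a wrong dispersion form. Sandwich standard errors gave 0.938-0.955 under lognormal frailty in both models. This stands as a separate matter.

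The rule limiting pre-randomisation data to description is the weaker objection. Read literally, it would also exclude covariates the plan already uses: the baseline 8-point profiles come from the two days before Visit 14 (Protocol 8.7.1), and baseline CGM from the 11 to 13 days before randomisation (Appendix B 4.1). The rule needs clarifying, but it is not a reason against adjustment.

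**Conclusion.** The omission is confirmed. It is a possible loss of precision, not an error. For 2 to 20 episodes per subject-year and frailty variance 1, adding the run-in rate would reduce the model standard error by nothing at correlation 0, up to about 2% at 0.3, 2-7% at 0.5 and 3-15% at 0.7. The true figure depends on the episode rate, the dispersion and the between-period correlation, none of which the documents give. No confirmatory conclusion, sample size or power statement changes. This is an optional improvement: a small and uncertain benefit at low cost.

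**What to change.** Before unblinding:

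- Add log((run-in count + 0.5)/run-in time) for the matching episode category to the models for all, daytime and nocturnal severe or BG confirmed episodes.
- Count the full run-in: onset from Visit 2 up to the day before the first randomised dose. An episode is treatment emergent if its onset "occurs on or after the first day of treatment with investigational medicinal product (IMP) after randomisation", so this boundary prevents counting any episode twice.
- Define this count as the baseline for these models, and state that the rule on pre-randomisation data does not bar baseline covariates.
- Keep the planned model as a sensitivity analysis, and leave the severe-only model unchanged.

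The cost is a few SAP sentences, one derived covariate per model and one extra run; no new data are needed. The rate ratio becomes conditional on the run-in rate, and two sets of ratios are reported. If the sponsor prefers the planned model, a sentence giving the reason would be enough.
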